6.1.1.1 Medical History

A medical history will be obtained by the Investigator or qualified designee at the time of Screening. Medical history will include all active conditions, and any other past conditions, as well as surgical procedures, that are considered to be clinically significant by the Investigator and/or occurred within the 12 weeks prior to Screening. Illnesses first occurring or detected after the signing of the informed consent, or during the study and/or worsening of an existing illness in severity, frequency or nature after signing of the informed consent are to be documented as AEs on the CRF. Prior treatments, defined as administered up to 12 weeks prior to the time of informed consent and stopped prior to dosing on Day 0, should be recorded in the CRF as prior medications. Concomitant treatments, defined as continuing or new treatments taken at or after the signing of the informed consent, should be recorded in the CRF as concomitant medications.

6.1.2 CLINICAL TRIAL EVALUATIONS AND PROCEDURES

Once eligibility has been confirmed, the participant will be assigned to receive IP. Visit dates and windows must be calculated from Day 0, unless otherwise noted. All study groups in Part 1 will be followed until Week 48, booster dose participants in Part 2 will be followed to Week 68 and all other participants in Part 2 who did not receive booster dose will be followed to Week 48. All participants will be followed in accordance with assessments outlined below.

6.1.2.1 Day 0

The following evaluations will be performed on **Day 0 prior to IP administration**:

- Collect all present and/or new or ongoing adverse events;
- Document any present conditions and concomitant illnesses;
- Record current concomitant medications/treatments ([Section 6.4.7](#));
- Targeted physical examination ([Section 6.4](#));
- Record vital signs ([Section 6.4](#));
- Collect urine for urine pregnancy test ([Section 6.4](#));
- Collect whole blood and serum for immunology assessment ([Section 6.4.6](#)).

The following evaluation will be performed on **Day 0 prior to EP**:

- Assess for injection site for IP leakage ([Section 6.4.1](#))

The following evaluations will be performed on **Day 0 after IP plus EP administration**:

- Collect any new adverse events;
- Download EP Data ([Section 6.4.1.1](#)).

6.1.2.2 Week 2

Calculated from Day 0, the following evaluations will be performed at this visit:

- Collect all present and/or new or ongoing adverse events;
- Document any present conditions and concomitant illnesses;
- Record current concomitant medications/treatments ([Section 6.4.7](#));
- Targeted physical examination ([Section 6.4](#));
- Record vital signs ([Section 6.4](#));
- Collect blood for CBC with differential, serum chemistry and liver function ([Section 6.4](#));
- Collect urine for routine urinalysis ([Section 6.4](#));
- Collect whole blood and serum for immunology assessment ([Section 6.4.6](#)).

6.1.2.3 Week 4

Part 1

The following evaluations will be performed on **Week 4 (complete prior to IP administration for Part 1 Study Groups A, B, E, F and I)**:

- Collect all present and/or new or ongoing adverse events;
- Document any present conditions and concomitant illnesses;
- Record current concomitant medications/treatments ([Section 6.4.7](#));
- Targeted physical examination ([Section 6.4](#));
- Record vital signs ([Section 6.4](#));

- Collect urine for urine pregnancy test ([Section 6.4](#)) for Part 1 Study Groups A, B, E, F and I only.

The following evaluation will be performed on **Week 4 prior to EP (for Part 1 Study Groups A, B, E, F and I only)**:

- Assess for injection site for IP leakage ([Section 6.4.1](#))

The following evaluations will be performed on **Week 4 after IP administration (for Part 1 Study Groups A, B, E, F and I only)**:

- Collect any new adverse events;
- Download EP Data ([Section 6.4.1.1](#)).

Part 2 if Day 0/Week 4 Dosing Regimen is Optimal

The following evaluations will be performed on **Week 4 (complete prior to IP administration if following Table 5)**:

- Collect all present and/or new or ongoing adverse events;
- Document any present conditions and concomitant illnesses;
- Record current concomitant medications/treatments ([Section 6.4.7](#));
- Targeted physical examination ([Section 6.4](#));
- Record vital signs ([Section 6.4](#));
- Collect urine for urine pregnancy test ([Section 6.4](#)).

The following evaluation will be performed on **Week 4 prior to EP (if following Table 5 only)**:

- Assess for injection site for IP leakage ([Section 6.4.1](#))

The following evaluations will be performed on **Week 4 after IP administration (if following Table 5 only)**:

- Collect any new adverse events;
- Download EP Data ([Section 6.4.1.1](#)).

Part 2 if Day 0/Week 8 Dosing Regimen is Optimal

The following evaluation will be collected on **Week 4 (if following Table 6 only)** during a follow-up phone call visit:

- Collect all present and/or new or ongoing adverse events.

6.1.2.4 Week 6

Calculated from Week 4 if Week 4 is a dosing visit, the following evaluations will be performed at this visit for **Part 1 and Part 2 if Day 0/Week 4 dosing regimen is optimal**:

- Collect all present and/or new or ongoing adverse events;
- Document any present conditions and concomitant illnesses;
- Record current concomitant medications/treatments ([Section 6.4.7](#));
- Targeted physical examination ([Section 6.4](#));
- Record vital signs ([Section 6.4](#));
- Collect blood for CBC with differential, serum chemistry and liver function ([Section 6.4](#));
- Collect urine for routine urinalysis ([Section 6.4](#));

- Collect whole blood and serum for immunology assessment ([Section 6.4.6](#)).

6.1.2.5 Week 8

Part 1

The following evaluations will be performed on **Week 8 (complete prior to IP administration for Part 1 Study Groups C, D, G and H)**:

- Collect all present and/or new or ongoing adverse events;
- Document any present conditions and concomitant illnesses;
- Record current concomitant medications/treatments ([Section 6.4.7](#));
- Targeted physical examination ([Section 6.4](#));
- Record vital signs ([Section 6.4](#));
- Collect urine for urine pregnancy test ([Section 6.4](#)) for Part 1 Study Groups C, D, G and H only.

The following evaluation will be performed on **Week 8 prior to EP (for Part 1 Study Groups C, D, G and H only)**:

- Assess for injection site for IP leakage ([Section 6.4.1](#))

The following evaluations will be performed on **Week 8 after IP administration (for Part 1 Study Groups C, D, G and H only)**:

- Collect any new adverse events;
- Download EP Data ([Section 6.4.1.1](#)).

Part 2 if Day 0/Week 4 Dosing Regimen is Optimal

The following evaluation will be collected on **Week 8 (if following Table 5 only)** during a follow-up phone call visit:

- Collect all present and/or new or ongoing adverse events.

Part 2 if Day 0/Week 8 Dosing Regimen is Optimal

The following evaluations will be performed on **Week 8 (complete prior to IP administration if following Table 6)**:

- Collect all present and/or new or ongoing adverse events;
- Document any present conditions and concomitant illnesses;
- Record current concomitant medications/treatments ([Section 6.4.7](#));
- Targeted physical examination ([Section 6.4](#));
- Record vital signs ([Section 6.4](#));
- Collect urine for urine pregnancy test ([Section 6.4](#)).

The following evaluation will be performed on **Week 8 prior to EP (if following Table 6 only)**:

- Assess for injection site for IP leakage ([Section 6.4.1](#))

The following evaluations will be performed on **Week 8 after IP administration (if following Table 6 only)**:

- Collect any new adverse events;
- Download EP Data ([Section 6.4.1.1](#)).

6.1.2.6 Week 10

Calculated from Week 8 if Week 8 is a dosing visit, the following evaluations will be performed at this visit for **Part 1 and Part 2 if Day 0/Week 8 dosing regimen is optimal:**

- Collect all present and/or new or ongoing adverse events;
- Document any present conditions and concomitant illnesses;
- Record current concomitant medications/treatments ([Section 6.4.7](#));
- Targeted physical examination ([Section 6.4](#));
- Record vital signs ([Section 6.4](#));
- Collect blood for CBC with differential, serum chemistry and liver function ([Section 6.4](#));
- Collect urine for routine urinalysis ([Section 6.4](#));
- Collect whole blood and serum for immunology assessment ([Section 6.4.6](#)).

6.1.2.7 Week 12

The following evaluations will be performed at this visit:

- Collect all present and/or new or ongoing adverse events;
- Document any present conditions and concomitant illnesses;
- Collect whole blood and serum for immunology assessment ([Section 6.4.6](#)).

6.1.2.8 Week 30

The following evaluations will be collected during the follow-up phone call visit:

- Collect all present and/or new or ongoing adverse events.

6.1.2.9 Week 48

Part 1

The following evaluations will be performed at this visit (End of Study visit):

- Collect all present and/or new or ongoing adverse events;
- Document any present conditions and concomitant illnesses;
- Record current concomitant medications/treatments ([Section 6.4.7](#));
- Full physical examination ([Section 6.4](#));
- Record vital signs ([Section 6.4](#));
- Collect blood for CBC with differential, serum chemistry and liver function ([Section 6.4](#));
- Collect urine for routine urinalysis ([Section 6.4](#));
- Collect whole blood and serum for immunology assessment ([Section 6.4.6](#)).

Part 2

The Week 48 visit will be the End of Study visit for participants receiving only two doses. The Week 48 visit will be the last dosing visit for participants receiving three doses. The following evaluations will be performed on **Week 48 (complete prior to IP administration for Part 2 participants receiving a third/booster dose):**

- Collect all present and/or new or ongoing adverse events;
- Document any present conditions and concomitant illnesses;
- Record current concomitant medications/treatments ([Section 6.4.7](#));

- Targeted physical examination ([Section 6.4](#)) for Part 2 participants receiving a third/booster dose;
- Full physical examination ([Section 6.4](#)) for Part 2 participants receiving two doses only;
- Record vital signs ([Section 6.4](#));
- Collect blood for CBC with differential, serum chemistry and liver function ([Section 6.4](#));
- Collect urine for routine urinalysis ([Section 6.4](#));
- Collect urine for urine pregnancy test ([Section 6.4](#)) for Part 2 participants receiving a third/booster dose;
- Collect whole blood and serum for immunology assessment ([Section 6.4.6](#)).

The following evaluation will be performed on **Week 48 prior to EP (for Part 2 participants receiving a third/booster dose only)**:

- Assess for injection site for IP leakage ([Section 6.4.1](#))

The following evaluations will be performed on **Week 48 after IP administration (for Part 2 participants receiving a third/booster dose only)**:

- Collect any new adverse events;
- Download EP Data ([Section 6.4.1.1](#)).

6.1.2.10 Week 50

The following evaluations will be performed at this visit **only for Part 2 participants receiving a third/booster dose**:

- Collect all present and/or new or ongoing adverse events;
- Document any present conditions and concomitant illnesses;
- Record current concomitant medications/treatments ([Section 6.4.7](#));
- Targeted physical examination ([Section 6.4](#));
- Record vital signs ([Section 6.4](#));
- Collect blood for CBC with differential, serum chemistry and liver function ([Section 6.4](#));
- Collect urine for routine urinalysis ([Section 6.4](#));
- Collect whole blood and serum for immunology assessment ([Section 6.4.6](#)).

6.1.2.11 Week 68

The following evaluations will be performed at this visit (End of Study Visit) **only for Part 2 participants receiving a third/booster dose**:

- Collect all present and/or new or ongoing adverse events;
- Document any present conditions and concomitant illnesses;
- Record current concomitant medications/treatments ([Section 6.4.7](#));
- Full physical examination ([Section 6.4](#));
- Record vital signs ([Section 6.4](#));
- Collect blood for CBC with differential, serum chemistry and liver function ([Section 6.4](#));
- Collect urine for routine urinalysis ([Section 6.4](#));
- Collect whole blood and serum for immunology assessment ([Section 6.4.6](#)).

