Urinalysis Routine ^f	X			X			X				X		X	X
Pregnancy Test ^g	X	X			X						X ⁱ			
INO-4700 or placebo + EP ^h		X			X						X ⁱ			
Download EP Data ^j			X			X						X ⁱ		
Adverse Events ^k	X	X	X	X	X	X	X	X	X	X	X ⁱ		X	X
Immunology (Whole blood) ^l	X	X					X		X		X		X	X
Immunology (Serum) ^m	X	X					X		X		X		X	X

- a. Screening assessment occurs from -60 days to -1 day prior to Day 0. If screening occurs within 14 days prior to Day 0, then do not repeat medical history prior to dosing.
- b. Follow-up phone call to collect AEs.
- c. Full physical examination at screening and Week 48 (participants receiving only two doses) or Week 68 (participants receiving three doses), as well as any other study discontinuation visit. Targeted physical exam at all other visits.
- d. Includes Na, K, Cl, HCO₃ or CO₂, Ca, PO₄, glucose, BUN, Cr, AST and ALT.
- e. MERS-CoV antibody (per PI discretion), HIV antibody or rapid test, HBsAg, HCV antibody.
- f. Dipstick for glucose, protein, and hematuria. Microscopic examination should be performed if dipstick is abnormal.
- g. Serum pregnancy test at screening. Urine pregnancy test prior to dosing at other visits.
- h. INO-4700 or placebo is prepared by unblinded pharmacy personnel. All doses delivered via ID injection followed by EP.
- i. Complete only for participants receiving a third dose of either INO-4700 or placebo (Part 2B).
- j. Following administration of INO-4700 or placebo, EP data will be downloaded from the CELLECTRA™ 2000 device and provided to Inovio.
- k. Includes AEs from the time of consent and all injection site reactions that qualify as an AE.
- l. 4 x 8.0 mL (32 mL) whole blood Cell Preparation Tubes (CPT) per time point. Note: At the investigator's discretion, rather than collecting a sample at screening, 64 mL (8 x 8.0 mL whole blood in CPT tubes) may be collected prior to dosing on Day 0.
- m. 1 x 8 mL blood in 10 mL red top serum collection tube per time point. Note: Collect four aliquots of 1 mL each (total 4 mL) serum at each time point prior to 1st dose. At the investigator's discretion, rather than collecting a sample at screening, 2 x 8 mL blood in two (2) 10 mL red top serum collection tubes (for eight aliquots of 1 mL each) may be collected prior to dosing on Day 0.

TABLE 6 – PART 2 TRIAL SCHEDULE OF EVENTS (DAY 0 & WEEK 8 OPTIMAL REGIMEN)

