All Part 1 participants will be followed for 48 weeks from the Day 0 dosing [i.e., Week 48 will be the planned End of Study (EOS) visit].

Part 2 – Expansion

In Part 2, approximately 350 participants will be evaluated across one (1) dose level and regimen as outlined in [Table 2](#) and [Table 3](#). The dose level and regimen will be identified based on the optimal dose selection from Part 1. Enrollment into Part 2 may begin following completion of the Week 10 optimal dose and regimen selection in Part 1 (i.e., prior to Week 48 completion in Part 1).

In Part 2A, participants will be randomized to receive the optimal dose of active (INO-4700) selected in Part 1 of this study or placebo (SSC-0001) ([Figure 1](#)). Approximately 300 participants will receive INO-4700 and 50 participants will receive placebo.

In Part 2B, the first 200 participants randomized to the Part 2A Active Study Group will receive a third dose of either INO-4700 or placebo at Week 48. Specifically, Study Group “Active – Booster” will receive INO-4700 at the first (Day 0), second (Week 4 or 8) and third (booster at Week 48) doses. Study Group “Active – Placebo” will receive INO-4700 at the first (Day 0) and second (Week 4 or 8) doses, and placebo at the third (Week 48) dose. Similarly, in Part 2B, the first 25 participants randomized to the Part 2A Placebo Study Group will receive a third dose of placebo at Week 48. Collectively, these first 225 participants will be followed for 68 weeks from the Day 0 dosing [i.e., Week 68 will be the planned End of Study (EOS) visit]. All remaining 125 participants in Part 2A (i.e., those receiving only 2 doses) will be followed for 48 weeks from the Day 0 dosing [i.e., Week 48 will be the planned End of Study (EOS) visit].

All participants and all clinical site staff will remain blinded to the subject treatment allocation (i.e., INO-4700 or placebo), with the exception of the site’s pharmacy personnel. Enrollment into Active and Placebo Study Groups will proceed in parallel. No enrollment pauses are planned.

Upon completion of the Week 12 visit and availability of immunological and safety data, group-level (INO-4700 or placebo) unblinded summaries of immunogenicity and safety will be produced. This Week 12 analysis will serve to inform product development goals. The Sponsor will continue to remain blinded to subject-level treatment allocation (i.e., INO-4700 or placebo) for the remainder of the trial.

DSMB for Parts 1 and 2

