4.3 DISCONTINUATION/WITHDRAWAL OF CLINICAL TRIAL PARTICIPANTS

Participants may withdraw consent at any time for any reason or be dropped from the trial at the discretion of the Investigator should any untoward effect occur. In addition, the Investigator or the Sponsor has the right to withdraw a subject from the trial at any time.

The Investigator must notify the Sponsor immediately when a subject has been discontinued/withdrawn due to an Adverse Event (AE). If a subject discontinues from the trial or is withdrawn from the trial prior to trial completion, all applicable activities scheduled for the final trial visit (i.e., Part 1 Week 48 EOS or Part 2 Week 48 or 68 EOS) should be performed at the time of discontinuation. Any AEs and/or Serious Adverse Events (SAEs) present at the time of discontinuation/withdrawal should be followed in accordance with the safety requirements outlined in [Section 7.9: Safety Data Reporting Period, Method of Collection and Submission](#).

Unless a subject refuses to continue participation, all follow-up visits and procedures should be completed as indicated in the Schedule of Events (Tables 3, 4 and 5) following the last dose whether or not the subject has completed all doses.

Reasons for withdrawal from the trial may include but are not limited to the following:

- Subject withdrawal of consent at any time
- Any medical condition that the Investigator or Sponsor determines may jeopardize the subject's safety if he or she continues in the trial
- Investigator, DSMB or Sponsor determines it is in the best interest of the subject
- Subject non-compliance

Every effort should be made to obtain information on participants who withdraw from the trial. The primary reason for withdrawal from the trial should be documented on the appropriate eCRF. However, participants will not be followed for any reason after consent has been withdrawn. Data and/or samples collected prior to withdrawal of consent will be analyzed.

Subject dosing may be discontinued if they experience any of the following:

- Adverse Event (Adverse Reaction)
 - The Investigator or trial coordinator must notify the Sponsor immediately when a subject has been discontinued/withdrawn due to an Adverse Event (AE).
- Any medical condition that may jeopardize the subject's safety if he or she continues on trial
- Pregnancy

Subjects who discontinue or withdrawal from the study will not be replaced.

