6.1.2 CLINICAL TRIAL EVALUATIONS AND PROCEDURES

Once eligibility has been confirmed, the participant will be assigned to receive IP. Visit dates and windows must be calculated from Day 0, unless otherwise noted. All study groups in Part 1 will be followed until Week 48, booster dose participants in Part 2 will be

followed to Week 68 and all other participants in Part 2 who did not receive booster dose will be followed to Week 48. All participants will be followed in accordance with assessments outlined below.

6.1.2.1 Day 0

The following evaluations will be performed on **Day 0 prior to IP administration**:

- Collect all present and/or new or ongoing adverse events;
- Document any present conditions and concomitant illnesses;
- Record current concomitant medications/treatments ([Section 6.4.7](#));
- Targeted physical examination ([Section 6.4](#));
- Record vital signs ([Section 6.4](#));
- Collect urine for urine pregnancy test ([Section 6.4](#));
- Collect whole blood and serum for immunology assessment ([Section 6.4.6](#)).

The following evaluation will be performed on **Day 0 prior to EP**:

- Assess for injection site for IP leakage ([Section 6.4.1](#))

The following evaluations will be performed on **Day 0 after IP plus EP administration**:

- Collect any new adverse events;
- Download EP Data ([Section 6.4.1.1](#)).

6.1.2.2 Week 2

Calculated from Day 0, the following evaluations will be performed at this visit:

- Collect all present and/or new or ongoing adverse events;
- Document any present conditions and concomitant illnesses;
- Record current concomitant medications/treatments ([Section 6.4.7](#));
- Targeted physical examination ([Section 6.4](#));
- Record vital signs ([Section 6.4](#));
- Collect blood for CBC with differential, serum chemistry and liver function ([Section 6.4](#));
- Collect urine for routine urinalysis ([Section 6.4](#));

6.1.2.3 Week 4

Part 1

The following evaluations will be performed on **Week 4 (complete prior to IP administration for Part 1 Study Groups A, B, E, F and I)**:

- Collect all present and/or new or ongoing adverse events;
- Document any present conditions and concomitant illnesses;
- Record current concomitant medications/treatments ([Section 6.4.7](#));
- Targeted physical examination ([Section 6.4](#));
- Record vital signs ([Section 6.4](#));
- Collect urine for urine pregnancy test ([Section 6.4](#)) for Part 1 Study Groups A, B, E, F and I only.

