- Collect urine for routine urinalysis ([Section 6.4](#));
- Collect whole blood and serum for immunology assessment ([Section 6.4.6](#)).

6.1.2.7 Week 12

Part 1

The following evaluations will be collected during the follow-up phone call visit:

- Collect all present and/or new or ongoing adverse events.

Part 2 if Day 0/Week 4 Dosing Regimen is Optimal

The following evaluations will be performed at this visit:

- Collect all present and/or new or ongoing adverse events;
- Document any present conditions and concomitant illnesses;
- Collect whole blood and serum for immunology assessment ([Section 6.4.6](#)).

Part 2 if Day 0/Week 8 Dosing Regimen is Optimal

The following evaluations will be collected during the follow-up phone call visit:

- Collect all present and/or new or ongoing adverse events.

6.1.2.8 Week 30

The following evaluations will be collected during the follow-up phone call visit:

- Collect all present and/or new or ongoing adverse events.

6.1.2.9 Week 48

Part 1

The following evaluations will be performed at this visit (End of Study visit):

- Collect all present and/or new or ongoing adverse events;
- Document any present conditions and concomitant illnesses;
- Record current concomitant medications/treatments ([Section 6.4.7](#));
- Full physical examination ([Section 6.4](#));
- Record vital signs ([Section 6.4](#));
- Collect blood for CBC with differential, serum chemistry and liver function ([Section 6.4](#));
- Collect urine for routine urinalysis ([Section 6.4](#));
- Collect whole blood and serum for immunology assessment ([Section 6.4.6](#)).

Part 2

The Week 48 visit will be the End of Study visit for participants receiving only two doses. The Week 48 visit will be the last dosing visit for participants receiving three doses. The

following evaluations will be performed on **Week 48 (complete prior to IP administration for Part 2 participants receiving a third/booster dose)**:

- Collect all present and/or new or ongoing adverse events;
- Document any present conditions and concomitant illnesses;
- Record current concomitant medications/treatments ([Section 6.4.7](#));
- Targeted physical examination ([Section 6.4](#)) for Part 2 participants receiving a third/booster dose;
- Full physical examination ([Section 6.4](#)) for Part 2 participants receiving two doses only;
- Record vital signs ([Section 6.4](#));
- Collect blood for CBC with differential, serum chemistry and liver function ([Section 6.4](#));

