8.4 ANALYTICAL POPULATIONS

Analysis populations will be:

The modified intention to treat (mITT) population includes all participants who receive at least one dose of the INO-4700 or placebo. Participants in this sample will be analyzed by their original assigned dose of INO-4700 or placebo. The mITT population will be used to analyze co-primary and exploratory immunological endpoints.

The per-protocol (PP) population is comprised of mITT participants who receive all their planned administrations and who have no Medical Monitor-assessed important protocol violations. Analyses on the PP population will be considered supportive of the corresponding mITT analyses. Participants excluded from the PP population will be identified and documented prior to locking the study database.

The safety analysis population includes all participants who receive at least one dose of INO-4700 or placebo administered by ID injection. Participants for this population will be grouped in accordance with the dose of INO-4700 or placebo that they received. This population will be used for all safety analyses in the study.

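### Part 2B follow-up to Week 68 goes by assignment in some sections and by receipt of the third dose in others, so a site could discharge an assigned participant at Week 48 if the dose is withheld

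*Protocol*

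**What the plan says.** All references are to Protocol v2.0 unless noted.

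**By order of randomisation.** Section 3.0 takes the first 200 active and first 25 placebo participants and states: "Collectively, these first 225 participants will be followed for 68 weeks from the Day 0 dosing". The others are covered by: "All remaining 125 participants in Part 2A (i.e., those receiving only 2 doses) will be followed for 48 weeks". Section 8.2 gives the same split, and SAP 1.2.2 ties the 68 weeks to the randomised regimen.

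**By receipt.** Section 6.1.2 states that "all other participants in Part 2 who did not receive booster dose will be followed to Week 48". Section 6.1.2.9 adds: "The Week 48 visit will be the End of Study visit for participants receiving only two doses". Sections 6.1.2.10 and 6.1.2.11 restrict the Week 50 and Week 68 visits to those getting a third dose. In Tables 5 and 6, footnote i is attached to the Week 50 and Week 68 column headings, so it governs every assessment in them: "Complete only for participants receiving a third dose of either INO-4700 or placebo (Part 2B"). SAP Tables 1-2 and 1-3 repeat it.

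**Both at once.** SAP 1.2.1 describes the Week 68 group as those receiving a third dose and, in the same sentence, counts them as 225.

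**Missed doses.** Section 4.3 requires follow-up visits to be completed "following the last dose whether or not the subject has completed all doses", unless the participant refuses. It does so by reference to the Schedule of Events, cited as Tables 3, 4 and 5. The schedules are Tables 4, 5 and 6.

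**Analysis.** Section 8.4 says of the mITT population: "Participants in this sample will be analyzed by their original assigned dose of INO-4700 or placebo". Section 8.5.8 rules out imputation.

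**The concern.** The two definitions agree only if every one of the 225 receives the third dose. The protocol itself foresees cases where that dose is not given: dosing stopped for an adverse event or medical condition (4.3), a discussion with the sponsor after an adverse event of special interest (7.9), or the steroid and vaccine restrictions (6.4.8). For such a participant, Section 3.0 expects visits to Week 68, while the visit text and footnote i schedule none after Week 48.

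Three things are at stake:

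- **Safety.** Someone whose dosing stopped for a health reason could lose up to 20 weeks of observation for new-onset events, along with the laboratory tests at Weeks 50 and 68.
- **Persistence.** Immunology samples at those visits would not be drawn, although the participant has had INO-4700 or placebo at the earlier doses.
- **Analysis by assignment.** With no imputation, mITT summaries at Weeks 50 and 68 would contain dose recipients only, under a label that says otherwise.

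**Working it through.** **1. The plan's own counts.** From Tables 2 and 3: 100 + 100 + 25 = 225 to Week 68. The remainder is 350 − 225 = 125 to Week 48 (300 − 200 = 100 active, 50 − 25 = 25 placebo). Both stated figures reproduce. They are planned numbers by assignment.

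**2. An assigned participant whose third dose is withheld.**

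| Text | Where it leads |
|---|---|
| 3.0, 8.2, SAP 1.2.2 | Week 68, as one of the first 225 |
| 6.1.2, 6.1.2.9–6.1.2.11, footnote i | Week 48 is End of Study; no Week 50 or 68 visit |
| 4.3 | Follow-up continues, but as the schedule indicates, which returns to footnote i |
| 6.4 (pregnancy testing) | Attempt to follow for the rest of the study |
| 7.11 (pregnancy) | Safety follow-up to trial discharge; 6.4 places discharge at Week 48 or Week 68, so this does not say which |
| 7.8.1.1 (unfit to dose after COVID-19) | Safety follow-up for the rest of the trial |
| 7.9 | SAEs and AESIs followed to resolution or stabilisation, even past the reporting period |

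Pregnancy and COVID-19 therefore have text that points to continued follow-up, and SAEs and AESIs already under way are not dropped. Other adverse events or medical conditions, and the steroid and vaccine restrictions, have only Section 4.3, which leads back to the schedule.

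**3. Length of the gap.** 68 − 48 = 20 weeks.

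**4. Number affected.** Let w be the share of the 225 whose third dose is withheld. The documents give no value, so w is an assumption. Number affected = 225 × w. For the booster contrast (100 against 100), assume the same w in both arms and a common variance. Its standard error is then multiplied by √(1/(1 − w)).

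| Assumed w | 225 × w | Left per 100 | SE multiplier |
|---|---|---|---|
| 2% | 4.5 | 98 | 1.010 |
| 5% | 11.25 | 95 | 1.026 |
| 10% | 22.5 | 90 | 1.054 |
| 15% | 33.75 | 85 | 1.085 |

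These counts are for participants still willing to attend. Anyone who withdraws consent is lost under either rule (4.3).

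**5. Primary Part 2 test.** Exact binomial, n = 260, 70% against 80%, one-sided 0.025: the rule is at least 197 responders, exact type 1 error 0.0232, power 0.960. This agrees with the stated power above 90%. Nothing in the documents ties this test to Week 50 or Week 68 data, so the figure does not move.

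**The case against.** The strongest defence is that *receiving* is shorthand for the planned regimen. Section 3.0 glosses exactly 125 people as those receiving two doses, which can only be a planned count. SAP 1.2.1 equates third-dose recipients with 225. Footnote i carries the label Part 2B, a group that Section 3.0 defines by randomisation order. Section 4.3 is the specific rule for missed doses, and it would do nothing for a missed third dose if footnote i overrode it. This is a fair account of what the authors probably meant, and it rules out one inference a reader might draw: that everyone whose third dose is withheld must leave at Week 48. The documents do not go that far, particularly for pregnancy and COVID-19.

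It does not remove the ambiguity. No passage states what happens to an assigned participant who misses the third dose, and the site works from the schedule.

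Two other stronger inferences also fail:

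- A reader might take *booster* in Section 6.1.2 to mean INO-4700 only, so that everyone given placebo at Week 48 is discharged. Footnote i names placebo, Sections 6.1.2.9 to 6.1.2.11 speak of a third or booster dose, SAP 1.2.2 applies booster regimens to all 225, and Section 8.5.9 describes boosting with placebo.
- A reader might take the gap between 300 active participants and 260 evaluable as a non-receipt rate. Section 8.6 gives 260 as the sample for the response-rate test. It says nothing about the Week 48 dose.

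The mITT analysis also remains feasible on available data. What suffers is its claim to represent everyone assigned.

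**Conclusion.** The inconsistency is real and stands in the current protocol. Read literally, the schedule allows discharge at Week 48 of an assigned participant whose third dose is withheld for a reason that has no follow-up text of its own.

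The effect is small. On an assumed 2–15% non-receipt, about 5 to 34 of 225 participants could lose up to 20 weeks, and the standard error of the booster contrast rises by about 1–8.5%. That contrast is exploratory. Because its two arms are treated alike under blind until Week 48, the loss should cost precision and not add bias. The upper figures assume that every withheld dose ends in discharge, which Sections 4.3, 6.4, 7.8.1.1 and 7.11 make unlikely. Power of the primary Part 2 test is unchanged.

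The protocol administrative memo on discontinuation records that the trial would not proceed to Part 2, so no participant was affected. The correction matters for the design text and for any protocol that reuses it.

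**What to change.** State the follow-up set once, by assigned regimen. In Sections 6.1.2 and 6.1.2.9 to 6.1.2.11, footnote i of Tables 5 and 6, and SAP 1.2.1, define Week 50 and Week 68 data collection and the End of Study visit for participants *randomised to a three-dose regimen, whether or not the third dose is given*. Keep *receiving* only for the dosing, pre-dose pregnancy test and EP-download cells. Bring the matching phrases in Sections 3.5 and 3.6 and in SAP Tables 1-2 and 1-3 into line. Correct the citation in Section 4.3 to Tables 4, 5 and 6.

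No dosing or withholding rule changes. The cost is wording in two documents, plus two already-scheduled visits for the few participants concerned, who may still refuse them.
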